## 9. TREATMENT OF SUBJECTS

### 9.1. Study Drug Dose Rationale

Subjects will be dosed with peramivir at the dosage levels currently approved in the US package insert for peramivir. The standard dose will be a single IV dose of 600 mg for subjects with CrCL  $\geq$  50 ml/min and reduced for subjects with CrCL < 50 ml/min as described in Section 9.4.

### 9.2. Study Drug

Peramivir solution for infusion is a clear, iso-osmotic, sterile, nonpyrogenic solution in 200 mg per 20 mL (10 mg/mL) single-use glass vials fitted with rubber stoppers and aluminum flip-off seals. The drug product should be stored at room temperature (excursion permitted to 59° to 86°F).

### 9.3. Study Drug Preparation and Administration

The Principal Investigator at each study center will designate a pharmacist (or other qualified study staff member) to prepare IV peramivir.

Subjects will receive a single dose of 600 mg peramivir (or less if renally impaired) diluted in 0.9% saline, 0.45% saline, 5% dextrose or lactated Ringer's using the technique described in a separate drug preparation instruction sheet, administered IV over a period of 15 to 30 minutes. The calendar date and 24-hour clock time (start and end of the IV infusion) will be recorded.

The intravenous line used to administer peramivir must be flushed prior to and after peramivir administration. No other medications should be administered through the same IV line during peramivir administration.

### 9.4. Dose Adjustments for Subjects with Renal Impairment

Table 2 provides dose adjustments based on creatinine clearance for subjects with renal impairment. In subjects with chronic renal impairment maintained on hemodialysis, peramivir should be administered after dialysis at a dose adjusted based on renal function as shown in the table below.

**Table 2. Dosage Adjustment for Subjects with Altered Creatinine Clearance**

	Creatinine Clearance (mL/min) a		
	$\geq$ 50	30 to 49	10 to 29
Recommended Dose (mg)	600 mg	200 mg	100 mg

a Calculated using the Cockcroft -Gault equation.

### 9.5. Study medication accountability

The Investigator/pharmacist must maintain accurate records of the disposition of all study drug received from the Sponsor and administered to the subject (including date and time), and any drug accidentally destroyed. The Sponsor will supply a specific Drug Accountability Form. At the end of the study, information describing study drug supplies (e.g., lot numbers) and disposition of supplies for each subject must be provided, signed by the Investigator or designee, and collected by the Study Monitor. If any

errors or irregularities in any shipment of study medication to the site are discovered at any time, the Sponsor Project Manager must be contacted immediately.

Periodically during the trial and at the end of the study, all medication that was neither dispensed or administered, as well as packaging materials will be collected with supervision of the monitor and returned to the Sponsor or destroyed on site as dictated by the appropriate Standard Operating Procedure (SOP) at the participating site

#### **9.6. Randomization and Blinding/ Masking**

As this is a single-arm, open-label study, randomization and blinding are not applicable.

#### **9.7. Treatment Compliance**

Intravenous peramivir will be administered by study staff or other qualified personnel. Details of the infusion (to include date of dose, start time, and stop time) will be recorded by a member of the study staff on Day 1; treatment compliance is expected to be 100% for this study.

#### **9.8. Overdose and Toxicity Management**

To date there is no experience with overdose of IV peramivir. If overdose occurs, subjects should receive indicated supportive therapy and evaluation of hematologic and clinical chemistry laboratory tests should be conducted. Peramivir is cleared by hemodialysis; the decision to use hemodialysis should be addressed on a case-by-case basis with the Sponsor.

#### **9.9. Concomitant Medications**

With the exception of medications used for the symptomatic treatment of influenza-related symptoms, administration of any dose of a concomitant medication during the study period must be recorded by the study staff within the subject's study source documents (e.g., chart). This includes prescription medications as well as over-the-counter medications.

Medications, such as antipyretics and analgesics, used for the symptomatic treatment of influenza-related symptoms will be recorded separately. Subjects will record the type, date, and time of symptomatic medications in the subject diary supplied by BioCryst including the date and time of administration. Study staff will provide diary completion instructions to subjects during their first study visit.

Use of concomitant medications will be assessed and recorded at Screening, and daily throughout the duration of the study through the study completion visit at Day 14 or later.

##### **9.9.1. Antipyretics and Analgesics**

Resolution of fever is an important efficacy endpoint for this study. Accordingly, use of any antipyretics or analgesics with antipyretic properties must be carefully controlled and documented. Antipyretics and analgesics may be administered while the subject is enrolled in this study. The names and times of administration of these medications will be recorded by the subject/caregiver in the subject diary. To avoid the confounding effects of antipyretic medications, temperature measurements recorded by the subjects will be taken, whenever possible, at least 4 hours after administration of the antipyretic medication.

Continuation of low dose aspirin for cardioprophylaxis is allowed.

**9.9.2. Medications for Chronic Diseases/Conditions**

Subjects with chronic medical conditions may continue to receive prescribed treatments during participation in this protocol. For example, treatment for cardiovascular conditions, endocrine conditions, rheumatologic conditions, respiratory conditions, dermatologic conditions, and neurologic conditions may be continued if not otherwise contraindicated within this protocol.

**9.9.3. Antivirals**

Subjects must not have received any doses of oseltamivir, zanamivir, amantadine, or rimantadine in the 7 days prior to study drug administration. Concomitant use of oseltamivir, zanamivir, amantadine, and/or rimantadine is not permitted during administration of study drug and during the post-treatment follow-up period. Antivirals for other infections such as HIV or herpes simplex may be taken.

**9.9.4. Antibiotics**

Oral or parenteral antibiotics may be administered at any time after enrollment if medically indicated. If such use is a result of proven or suspected influenza-related complication, the appropriate assessments should be carried out (see Section [10.2.4](#)).

**9.9.5. Immunizations**

Subjects must not have received a live attenuated influenza vaccine in the 14 days prior to study drug administration. Immunizations of any kind should not be administered during study participation. Subjects who are candidates for pneumococcal immunization or other immunization should not receive such immunizations during the study period.

## 10. STUDY CONDUCT

### 10.1. Overview

Approximately 120 subjects will be enrolled in this open-label study (a minimum of 80 elderly subjects [ $\geq 65$  years] will be enrolled). A subject's duration of participation in this study is expected to be 14 days and will include up to 4 clinic visits. It is expected that most subjects will have the Screening visit and the Day 1 Treatment visit on the same day. Subjects will be discharged from this study on Day 14.

Additional, unscheduled visits may be required for subjects who report symptoms of influenza of moderate or severe intensity at Day 14 or have persistent adverse events and/or treatment-emergent laboratory findings that require medical monitoring or management.

All subjects will receive a single dose of IV peramivir (600 mg or reduced for renal impairment). Subjects will undergo follow-up clinical assessments on Days 3, 7, and 14.

An adequate nasal swab specimen will be collected from all enrolled subjects at Baseline (pre-dose) for virus subtype identification and quantitative virologic assessments and at the follow-up assessments on study Days 3, 7 and 14.

Specimens from all subjects yielding influenza virus will also be assessed for susceptibility to neuraminidase inhibitors (Day 1 and last specimen yielding influenza virus on culture). A central laboratory will perform all virologic assessments.

Up to 3 blood samples will be drawn to obtain plasma samples for drug concentration determinations, where possible, during the following time periods, beginning from the end of dosing until release from the site:

- One time point immediately following completion of the infusion
- One time point from 30 minutes to 1 hour post-infusion
- One time point from 1 hour to 3 hours post-infusion

Adverse events and concomitant medications will be monitored at each scheduled visit from the Screening assessment to final study visit. Clinical laboratory investigations (chemistries, hematology, and urinalysis) will be collected at Baseline, Day 7 and Day 14 visits. Safety and tolerability will be evaluated through assessments of AEs, laboratory analyses (clinical chemistry, hematology, and urinalysis), vital signs and physical examinations at the time points indicated in the schedule of assessments.

All subjects/caregivers will record the following information in a Subject Diary:

- Assessment of the presence and severity of each of 7 symptoms of influenza on a 4-point severity scale (0, absent; 1, mild; 2, moderate; 3, severe) at Screening, then twice daily through Day 13, and prior to the subject's clinic visit on Day 14 or until each symptom is 0 or 1 for 48 hours. Symptoms will be reviewed at each clinic visit.
- Temperature measurements (oral) will be taken with an electronic thermometer provided by the Sponsor, approximately every 12 hours until temperature normalizes for 48 hours (i.e. temperature without antipyretic is  $< 37.4^{\circ}\text{C} / 99.4^{\circ}\text{F}$  orally for 4 measurements). With the exception of the Screening/ Baseline measurement, all temperature measurements will be

obtained at least 4 hours after, or immediately before, administration of oral acetaminophen or other antipyretic medications, if taken.

- The type, date, and time of medications used for the symptomatic treatment of influenza-related symptoms.
- Assessment of the subject's ability to perform usual activities using a 0 to 10 visual analogue scale once daily through Day 14, where 0 = Unable to perform usual activities at all, and 10 = Able to perform all usual activities fully.

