Up to 3 blood samples will be drawn, where possible, during the following time periods, beginning from the end of dosing until release from the site:

- One time point immediately following completion of the infusion
- One time point from 30 minutes to 1 hour post-infusion
- One time point from 1 hour to 3 hours post-infusion

Adverse events and concomitant medications will be monitored at each scheduled visit from the Screening assessment to final study visit. Clinical laboratory investigations (chemistries, hematology, and urinalysis) will be collected at Baseline, and Day 7 visits. Day 14 clinical laboratory investigations will only be collected if Day 7 labs are in the opinion of the investigator, significantly abnormal or clinically changed from baseline. In addition, clinical laboratory investigations may be conducted at any time for patient management / safety reasons. Safety and tolerability will be evaluated through assessments of adverse events, laboratory analyses (clinical chemistry, hematology, and urinalysis), vital signs and physical examinations at the time points indicated in the schedule of assessments.

A subject's duration of participation in this study is expected to be approximately 14 days and will include up to 4 clinic visits. Subjects will be discharged from this study on Day 14. Additional, unscheduled visits may be required for subjects who report symptoms of influenza of moderate or severe intensity at Day 14 or have persistent adverse events and/or treatment-emergent laboratory findings that require medical monitoring or management.

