#### **10.1.2.5. Day 14 (End of Study)**

The Day 14 assessments will be performed as a clinic visit. The following procedures/assessments will be performed on Day 14 (+ 3 days) or at the time of early withdrawal, where possible:

- Measure vital signs (blood pressure, pulse rate, and respiration rate)
- Measure and record oral body temperature
- Perform a urine or serum pregnancy test (non-pregnant females of childbearing potential only)
- Conduct an assessment for the presence of possible IRC; if an IRC is suspected, a targeted physical exam should be conducted to confirm the absence or presence of the IRC
- Review the subject diary for completeness
- Collect a bilateral adequate nasal swab specimen for viral culture, quantitative PCR assay and susceptibility to neuraminidase inhibitors.
- Review and record concomitant medications
- If Day 7 labs are, in the opinion of the investigator, significantly abnormal or significantly changed from baseline, collect blood specimen for clinical chemistry and/or clinical hematology tests as specified in Sections [11.2.1](#) and [11.2.2](#) and a serum sample for future influenza antibody analysis.
- If Day 7 urinalysis is, in the opinion of the investigator, significantly abnormal or significantly changed from baseline, collect urine for urinalysis
- Review and record AEs

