### **13.9. Safety Analyses**

Adverse Events will be mapped to a Medical Dictionary for Regulatory Activities (MedDRA)-preferred term and system organ classification. The occurrence of treatment-emergent AEs (TEAEs) will be summarized by age group and treatment group using MedDRA-preferred terms, system organ classifications, and severity. All AEs will be listed for individual subjects showing both verbatim and preferred terms. Separate summaries of treatment-emergent SAEs and AEs related to study drug will be generated.

Descriptive summaries of vital signs and clinical laboratory results will be presented by age group, treatment group and study visit. Laboratory abnormalities will be graded according to the DAIDS Table for Grading Adverse Events for Adults and Pediatrics (Publish Date: December 2004 Clarification, 2009, see Section 16.2). The number and percentage of subjects experiencing treatment-emergent graded toxicities will be summarized overall and by age group. Laboratory toxicity shifts from baseline to post-baseline assessments will be summarized overall and by age group.

Previous and concomitant medications will be mapped to a WHO preferred term and drug classification. The number and percent of subjects taking concomitant medications will be summarized using preferred terms and drug classifications.

The number and percent of subjects experiencing influenza related complications will be summarized overall and by age group.

Subject disposition will be presented for all subjects. The number of subjects who completed the study and discontinued from the study will be provided. The reasons for early discontinuation also will be presented.

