5.3.3. Clinical Laboratory Assessments

Descriptive summaries of selected (quantitative) clinical laboratory results will be presented by study visit for each age group and overall. The clinical chemistry profile will include: albumin, alkaline phosphatase (ALP), alanine aminotransferase (ALT), aspartate aminotransferase (AST), bicarbonate, direct bilirubin, bilirubin, blood urea nitrogen, calcium, creatine kinase, chloride, creatinine, gamma glutamyl transferase, glucose, potassium, lactate dehydrogenase (LDH), magnesium, phosphate, protein, sodium, and urate. The hematology profile will include: basophils, basophils/leukocytes, eosinophils, eosinophils/leukocytes, hematocrit, hemoglobin, lymphocytes, lymphocytes/leukocytes, erythrocyte mean corpuscular hemoglobin, erythrocyte mean corpuscular hemoglobin concentration, erythrocyte mean corpuscular volume, monocytes, neutrophils, neutrophils/leukocytes, platelets, erythrocytes, and leukocytes. Laboratory abnormalities (toxicities) will be graded according to the Division of AIDS (DAIDS) Table for Grading Adverse Events for Adults and Pediatrics (Published Date: December 2004). The number and percentage of subjects who experience treatment-emergent toxicities will be summarized for each age group and overall. Laboratory toxicity shifts from baseline to Day 7 will be summarized for each age group and overall.

All laboratory toxicities that occurred before the initiation of study treatment or more than 14 days post study drug discontinuation will be excluded from the tables but will be included in the listings.

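### Three rules govern Day 14 laboratory samples, and the SAP's shift and toxicity tables leave out some values collected after, or instead of, Day 7

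*Protocol*

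**What the plan says.** **Collection.** The documents give three rules for laboratory samples at Day 14.

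- *All subjects.* Protocol 10.1: samples "will be collected at Baseline, Day 7 and Day 14 visits", with no condition.
- *Conditional.* Protocol synopsis: "Day 14 clinical laboratory investigations will only be collected if Day 7 labs are in the opinion of the investigator, significantly abnormal" (or changed from baseline). Protocol 10.1.2.5 agrees: "If Day 7 labs are, in the opinion of the investigator, significantly abnormal or significantly changed from baseline, collect blood specimen". Sections 11.2.1 and 11.2.2 say the same for chemistry and hematology, and 11.2.3 has a similar conditional repeat for urinalysis.
- *Not scheduled.* Protocol Table 1, SAP 1.1 and the schedule in SAP 1.2 place labs at Baseline, Day 7 and Early Withdrawal only. A footnote to both schedules allows labs at any visit for subject management or adverse event monitoring.

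**Visit window.** Table 1, Protocol 10.1.2.5 and SAP 1.2 allow Day 14 plus 3 days. The synopsis, under duration of treatment, gives plus or minus 2 days.

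**Analysis.** SAP 3.3.8 counts a laboratory abnormality as treatment-emergent if the grade rises at any post-baseline visit no later than 14 days after dosing. SAP 5.3.3 adds that toxicities "more than 14 days post study drug discontinuation will be excluded from the tables", although they stay in the listings. On shifts, Protocol 13.9 says: "Laboratory toxicity shifts from baseline to post-baseline assessments will be summarized overall and by age group". SAP 5.3.3 says: "Laboratory toxicity shifts from baseline to Day 7 will be summarized for each age group and overall". SAP 6 declares one change from the protocol, a count of antipyretic doses, and expects no others.

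**The concern.** Laboratory abnormality is part of the primary endpoint (Protocol 7.1.1), so the rules for which values are drawn and tabulated should be unambiguous. Three things are at stake.

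First, an abnormality can be found at any post-baseline visit, so a subject with a Day 14 sample has one more chance of being counted than a subject without one. If sites read the protocol differently, the reported incidence depends partly on that reading.

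Second, the limit for the toxicity table closes before the permitted Day 14 visit window does. Under the conditional rule, the subjects sampled late are those whose Day 7 results caused concern.

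Third, Protocol 11.2.1 and 11.2.2 provide for blood samples at an early-termination visit that falls before Day 7. A shift table confined to Day 7 has no place for them, nor for unscheduled or Day 14 values.

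**Working it through.** There is no planned figure to reproduce: SAP 3.1 states that no formal sample size calculation was done. The check is calendar arithmetic plus a comparison of the stated rules.

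**1. Toxicity limit against visit window.** SAP 3.3.8 defines Study Day as event date − Day 1 date + 1, so days after dose = Study Day − 1.

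| Study Day | Days after dose | Within the 14-day limit |
|---|---|---|
| 14 | 13 | yes |
| 15 | 14 | yes |
| 16 | 15 | no |
| 17 | 16 | no |

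- Window +3 days: Study Days 14 to 17. Days 16 and 17 fall outside, 2 of 4 permitted days.
- Window ±2 days: Study Days 12 to 16. Day 16 falls outside, 1 of 5 permitted days.

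These are calendar days, not shares of visits or subjects. The documents do not say how visits spread over the window.

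**2. Which outputs the limit reaches.** It reaches the graded toxicity table (SAP 9, Table 14.3.4.2). It does not reach the by-visit chemistry and hematology summaries (Tables 14.3.4.1.1 and 14.3.4.1.2): SAP 3.3.6 places values by nominal visit, and no day limit is stated for those tables. A Study Day 17 sample recorded as Day 14 stays in them.

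**3. Shift tables.** Tables 14.3.4.3.1 to 14.3.4.3.3 are titled baseline to Day 7. Taking the nominal visit label, a sample recorded as Early Withdrawal, unscheduled or Day 14 enters none of them. SAP 5.4 gives the SAP precedence over the protocol, so the analysis in Protocol 13.9 is replaced, and SAP 6 does not record it.

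**4. What a conditional Day 14 column would contain.** The documents give no rate of abnormal Day 7 results, so the flagged share q is assumed. Take the flagged subjects as the upper tail of one normally distributed analyte. Their Day 7 mean then lies φ(z₁₋q)/q standard deviations above the whole group, and their expected Day 14 mean is that figure times the Day 7 to Day 14 correlation r (assumed 0.5 or 0.8).

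| q | n of 120 | n of 80 elderly | Day 7 excess (SD) | Day 14 excess, r = 0.5 | Day 14 excess, r = 0.8 |
|---|---|---|---|---|---|
| 5% | 6 | 4 | 2.06 | 1.03 | 1.65 |
| 10% | 12 | 8 | 1.75 | 0.88 | 1.40 |
| 20% | 24 | 16 | 1.40 | 0.70 | 1.12 |
| 30% | 36 | 24 | 1.16 | 0.58 | 0.93 |

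As an example, at q = 10%: 0.1755/0.10 = 1.75 (to two decimals), and half of that is 0.88. Such a mean could not be read against the Baseline or Day 7 mean of all subjects.

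**The case against.** **Worsening outside Day 7 is still counted.** A reader might infer that an abnormality in a subject who withdraws before Day 7 disappears. It does not. SAP 3.3.8 admits any post-baseline visit through Study Day 15, so that worsening enters the treatment-emergent count. What is lost is its place in the shift cross-tabulation. This stands.

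**Days 16 and 17 do not leave all the safety tables.** That reading is tempting but unsupported: the laboratory limit governs graded toxicities, and by-visit summaries and listings keep the values. Moreover, under the conditional rule the subject already has a flagged Day 7 result inside the limit. A late repeat changes the toxicity table only if it brings a higher grade or a new analyte. This stands and keeps the effect small.

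**A selected Day 14 column is not specified.** A reader might infer that Day 14 summaries necessarily describe subjects chosen for abnormality. That needs both the conditional rule and a Day 14 column. SAP 5.3.3 names no visits, and under Protocol 10.1 the column would be unselected. The fair criticism is that the SAP leaves the display open.

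**The collection conflict is mainly one overview sentence.** Protocol 10.1 goes on to refer to the schedule of assessments, and the footnote on labs at any visit lets the schedule coexist with a conditional draw. No document shows that sites diverged. This limits the likely effect, but the unconditional sentence remains in the operative text. The precedence clause in SAP 5.4 settles analysis, not what sites collect.

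**The SAP's choices have reasons.** Day 7 is the only post-baseline laboratory visit that Table 1 schedules for every continuing subject, so a Day 7 shift gives a common denominator. The 14-day limit also matches the one for adverse events. Both are good reasons to keep the Day 7 display, but neither explains an undeclared change or a limit shorter than the permitted visit.

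**Conclusion.** The point holds in limited form, as something the sponsor should correct. Three defects are plain on the text:

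- three collection rules for Day 14 labs, together with two visit windows;
- a toxicity limit that ends at Study Day 15 while the Day 14 visit may run to Day 17 (or to Day 16 under ±2);
- shift tables narrowed from post-baseline assessments to Day 7 without being declared.

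The consequence is that a new or higher-grade abnormality at an on-time visit on Study Day 16 or 17 appears only in listings, and early-withdrawal, unscheduled and Day 14 values enter no shift table. The number of subjects affected cannot be derived from the documents. The 6 to 36 of 120 in a conditional Day 14 column rests on assumed flag rates of 5% to 30%. The statement about early-withdrawal values assumes that they keep their own visit label and are not mapped to Day 7.

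The study is descriptive and tests no hypothesis, so no error rate is at issue. The issue is the completeness and readability of the primary safety tables.

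**What to change.** Reconcile Protocol 10.1, the synopsis, Table 1, 10.1.2.5, 11.2 and SAP 1.1 and 1.2 so that one Day 14 laboratory rule and one Day 14 window apply. Which rule and which window is for the sponsor to settle. The SAP is dated 14 June 2018, after the protocol's estimated last-subject date of April 2018. If collection is already complete, the report should state which rules were in use and how many Day 14 samples were drawn.

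In the SAP:

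1. Add to 5.3.3 shifts from baseline to the worst post-baseline grade, including early-withdrawal and unscheduled values. Keep the Day 7 shift as the common-denominator display. If the wider shift is not added, declare the narrowing in section 6.
2. Extend the treatment-emergent laboratory window in 3.3.8 and 5.3.3 to take in any value from the Day 14 visit within its permitted window. Under +3 days that means 16 days after dose (Study Day 17); under ±2 days, 15 days (Study Day 16).
3. Name the visits in the by-visit laboratory tables. If Day 14 labs are conditional, list them and leave them out of the by-visit means, or show them labelled as conditional with their n.

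The cost is a few sentences and a small amount of extra programming. Reported abnormality counts may rise slightly, and the laboratory window would differ from the 14-day adverse event window, which a table footnote can explain. The SAP changes need no further samples.
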